### **Funding Sponsor**

Study is funded by Grant PRG 1255 (duration 2021-2025).

## **Summary**

Title: Retrospective population-based study on epidemiology of acute mesenteric ischemia in Estonia

Protocol number: AMI version1.0

Study Design/Methodology: Retrospective population-based study

Study duration: April 2021 until December 2022

Study Center: primary study center: Tartu University Hospital, patients from all hospitals in Estonia included.

Objectives: to describe epidemiologic features in adult patients with acute mesenteric ischemia

Number of subjects: 500

Eligibility criteria: all at least 18-year-old patients with acute mesenteric ischemia during years 2016-2020.

Study interventions: none

## Background

This study is a retrospective population-based study on epidemiology of acute mesenteric ischemia in Estonia.

Acute mesenteric ischemia (AMI) is a potentially fatal vascular emergency with overall mortality of 60-80% (1). Acute mesenteric ischemia comprises a group of pathophysiologic processes that have a common end point – insufficient blood supply to the bowel leading to bowel ischemia and if blood supply is not restored fast, to transmural bowel necrosis (infarction):

1. Occlusive mesenteric ischemia:
  - a. Arterial thrombosis
  - b. Arterial embolism
  - c. Venous thrombosis
2. Non-occlusive mesenteric ischemia (NOMI)

There are no previous studies about the incidence of acute mesenteric ischemia in Estonia.

Between 1970 and 1982 in Malmö (Sweden) autopsies were conducted on as many as 87% of the deceased in the population of approximately 250 000 inhabitants. They found that the annual incidence of AMI was 12 per 100 000 inhabitants. (2). There has not been comparable study to Malmö cohort.

Between 2009 and 2013 Kärkkäinen JM et al studied patients with acute abdomen and found that the incidence rate of AMI was 7,3/100 000/year. (3).

Considering that population is aging and AMI primarily affects elderly then potentially incidence of AMI should increase. However, abovementioned studies suggest that it may rather decrease. Reasons for that could be better control and treatment of comorbidities. For example such development has been shown for cardiovascular events. (4)(5).

There are no large studies about the risk factors of AMI, but the main etiologic factor is atherosclerosis. (6).

Beaulieu and colleagues found a total of 23744 hospital admissions for AMI registered in the Nationwide Inpatient Sample database from 2005 to 2009. Only 3% received an attempt of open or endovascular revascularization, while 17% were treated with bowel resection alone, and 80% received no intervention whatsoever. (7).

Meanwhile studies have shown that correct diagnosis in right time and subsequent adequate treatment could potentially save more than half of AMI patients. (8).

According to this acute mesenteric ischemia needs definitely greater interest and continuing studies to improve diagnostics and treatment.

## **Study objectives**

Primary objective:

To identify the incidence of AMI in adult hospitalized patients in Estonia during 2016-2020.

Secondary objectives:

To describe the phenotype of AMI.

To describe treatment modalities and outcome of AMI.

Results obtained from this study will be used for designing a prospective multi-center study about AMI.

## **Study design and methods**

Sample size

1. Previous studies (1-3) have found that incidence of AMI could be 6-12/100 000/year.
2. We do not have exact primary data about AMI in Estonia and that is why we could not calculate precise sample size. We assume that 500 patients with AMI is sufficient to describe also different subgroups (see above).
3. In view of prior we plan to analyze data from 5 years and will collect the most recent data (years 2016-2020).

Study data

To identify the patients of interest, we ask Estonian Health Insurance Fund to extract data for all cases where diagnostic and procedure codes covering acute mesenteric ischemia during years 2016-2020 have been documented.

Diagnostic codes (ICD-10) and procedure codes (NOMESCO) that cover acute mesenteric ischemia:

1. ICD-10: I74.0, I74.1, I74.8, I74.9, I81, K55.0, K55.1, K55.8, K55.9
2. NOMESCO: PCE30, PCF30, PCG30, PCH30, PCJ30, PCK30, PCN30, PCP30, PCQ30, PCR30, PCT30

We ask for the following information for each patient:

1. Number of case
2. Personal identification code
3. When and where (name of the hospital) this patient was hospitalized with respective diagnostic code

From these patients we will identify those who truly have AMI, based on the following criteria:

- Occlusive acute mesenteric ischemia:

- a. appropriate clinical presentation of life-threatening acute intestinal ischemia with
  - b. thrombosis or embolism of the mesenteric arteries or thrombosis of the mesenteric veins and
  - c. either presence of pathological intestinal findings on a computer tomography (CT) scan (bowel wall thickening, abnormal bowel wall enhancement, or luminal dilatation) or bowel necrosis identified at laparoscopy/laparotomy/autopsy.
- Nonocclusive mesenteric ischemia (NOMI):
    - a. acute intestinal ischemia based on clinical presentation pattern and
    - b. pathological intestinal findings on a CT scan or bowel necrosis on laparoscopy/laparotomy or autopsy
    - c. without significant (<70 %) obstruction of the superior or inferior mesenteric artery.

The primary data screening will be performed by the principal investigator using Estonian Health Information System.

For patients who likely had AMI, data collection from medical case charts will be initiated.

Data collection in different hospitals will be organized by the principal investigator.

Also, we ask from Estonian Health Insurance Fund the total number of adult patients admitted to different Estonian hospitals for years 2016-2020 to calculate the incidence of AMI in adult hospitalized patients.

From Estonian Causes of Death Registry we ask data about all cases of death of the patients with acute mesenteric ischemia in the final database and their death certificate diagnoses to identify mortality outcome.

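### The only planned denominator is adults admitted to hospital; adding a resident person-year rate would be a cheap way to make the result comparable with the rates that frame the study

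*Combined protocol and SAP*

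**What the plan says.** The Study objectives section sets the primary aim: "To identify the incidence of AMI in adult hospitalized patients in Estonia during 2016-2020". Under Study design and methods (Study data), the Health Insurance Fund will be asked for "the total number of adult patients admitted to different Estonian hospitals for years 2016-2020 to calculate the incidence of AMI in adult hospitalized patients". This is the only denominator in the protocol.

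The surrounding text speaks of populations. The Summary gives "Study Design/Methodology: Retrospective population-based study" and adds "patients from all hospitals in Estonia included". The Background states "There are no previous studies about the incidence of acute mesenteric ischemia in Estonia" and reports a Swedish cohort: "They found that the annual incidence of AMI was 12 per 100 000 inhabitants". In that cohort "autopsies were conducted on as many as 87% of the deceased". The Background also cites 7.3 per 100 000 per year from a study of acute abdomen, and it discusses whether ageing raises incidence or whether incidence is falling. The Sample size text uses 6-12 per 100 000 per year.

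The Statistical analysis section lists descriptive statistics, including a standard error. It names no rate and no confidence interval. The Database section assigns one study-ID per patient.

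**The concern.** A reader who comes to the plan through its title and Background expects a rate in the adult population of Estonia. The plan yields the share of admitted adults who had AMI. Both can be called incidence, but they have different denominators and answer different questions.

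What is at stake is how far the result can be used. By its own account the study fills a national gap. Followed as written, it would still leave Estonia without a rate in residents, and its main figure could not be compared with the per-inhabitant rate it cites. Nor could a share of admissions inform the Background's question about ageing, because it carries no information on how many people of each age were at risk.

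A smaller matter concerns the unit. The request does not say whether a person admitted in two years, or to two hospitals, counts once in the denominator, whereas cases are counted by patient.

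**Working it through.** **Inputs from the protocol.** 500 patients (Summary; Sample size); 5 years, 2016-2020 (Sample size); 6-12 per 100 000 per year (Sample size); 12 per 100 000 inhabitants and 7.3 per 100 000 per year (Background). The protocol gives neither the number of adult residents nor the number of admitted adults. Where these are needed below, they are assumptions shown as ranges.

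**1. The plan's own figure.** The 500 cannot be reproduced as a calculation. The Sample size text says that a precise size could not be calculated and that 500 is assumed to be enough. As a plausibility check only, population = (500/5)/rate:

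- at 12 per 100 000: 100/0.00012 = 833 333
- at 7.3 per 100 000: 100/0.000073 = 1 369 863
- at 6 per 100 000: 100/0.00006 = 1 666 667

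In the other direction, assuming 1.0-1.1 million adult residents, expected cases run from 0.00006 x 1.0 million x 5 = 300 to 0.00012 x 1.1 million x 5 = 660. The 500 lies inside that range.

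**2. Which denominators are planned.**

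| Section | Denominator or unit |
|---|---|
| Study objectives | adults in hospital |
| Study data | adults admitted, 2016-2020 |
| Background, Swedish cohort | inhabitants, per year |
| Background, acute-abdomen study | per 100 000 per year, base not spelled out |
| Sample size | per 100 000 per year, base not spelled out |
| Statistical analysis; Annex 1 | none |

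The first two rows agree with each other. Neither is on the scale of the cited rates.

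**3. Dependence on admission volume.** Let P = C/N, with cases C held constant.

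- N 10% lower in all five years: 1/0.9 = 1.111, so P rises by 11.1%.
- N 10% higher in all five years: 1/1.1 = 0.909, so P falls by 9.1%.
- N 10% lower in one year only, with equal yearly admissions: the five-year denominator is 4.9/5 = 0.98 of its former size, and 1/0.98 = 1.020, so P rises by about 2%.

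**4. Comparison with sampling error.** Exact Poisson 95% limits for 500 cases are chi-square(0.025; 1000)/2 = 457.1 and chi-square(0.975; 1002)/2 = 545.8. Relative to 500 these are -8.6% and +9.2%. The full width is (545.8 - 457.1)/500 = 17.7%. The 11.1% shift is therefore about one half-width, not the whole interval.

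**5. Illustration of the two scales (assumed totals).** Assume 1.0-1.1 million adult residents and 100 000-250 000 adults admitted per year.

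- Resident rate at 1.0 million: 500/(5 x 1.0 million) = 10.0 per 100 000 person-years (9.1-10.9).
- Resident rate at 1.1 million: 500/(5 x 1.1 million) = 9.1 (8.3-9.9).
- Hospital figure, 100 cases per year: 100/250 000 = 40 to 100/100 000 = 100 per 100 000 admitted adults.
- Ratio of scales: 1.0 million/250 000 = 4 to 1.1 million/100 000 = 11.

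The hospital figures in this step count each person once per year. If each person were counted once over the whole period, the denominator could not exceed the sum of the five yearly counts, and repeat admissions in different years would make it smaller and the figure larger. This is why the unit must be stated.

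**The case against.** The strongest reply is that the plan is consistent: the objective names hospitalized adults and the data request supplies that denominator. The figure can also serve the one stated use, "Results obtained from this study will be used for designing a prospective multi-center study about AMI". The population-based label can fairly describe case finding across all hospitals. The protocol sets no objective of comparing its figure with earlier rates, and the Background's remarks on ageing are not an objective either. All of this stands, and it is why the point is an improvement and not an error.

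Four stronger readings are tempting, and the documents do not support them:

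- A reader might infer that the title contradicts the denominator. It does not, because nationwide case finding is a reasonable meaning of the label.
- A reader might infer that admission volume biases the primary figure. Dependence on admissions is what a measure per admitted adult means. The objective asks for a single figure for 2016-2020, with no comparison between years or hospitals. No document supports a 10% shift, and a single such year moves the pooled figure by only about 2%.
- A reader might take the 4- to 11-fold gap as overestimation. It rests on assumed totals and shows two different measures, neither of them biased.
- A reader might back-solve the 500 to show that a resident denominator was intended. The 500 was assumed, so the back-calculation cannot show that.

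It is also true that a resident rate could be added at reporting, since it needs no new patient data, and that the primary denominator is already fixed. The gain from specifying the rate now is modest but real: its age range, population source and standard would be settled before the case count is known. Finally, the added rate would not be fully comparable with a cohort based on so many autopsies.

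**Conclusion.** The point holds as a cheap improvement. The plan's only denominator yields a proportion of hospital patients. It answers the stated objective but cannot be set beside the 12 per 100 000 inhabitants, the 7.3 or the 6-12 per 100 000 per year that introduce the study.

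That the resident rate is absent follows from the text alone. The 11.1% and 2% figures are arithmetic on hypothetical changes in volume, with cases held constant; the 2% also assumes equal yearly admissions. The comparison with sampling error assumes that 500 cases are found. The resident and hospital figures in step 5 rest on assumed totals and serve only to show that the scales differ.

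No patient data are affected and the planned figure remains valid for what it is. What would be gained is a first resident rate for Estonia.

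**What to change.** - **Study objectives and Study data:** keep the hospital figure, but call it a proportion. Count its numerator and denominator in the same stated unit, for example unique persons over 2016-2020.
- **Same sections:** add hospital-diagnosed AMI per 100 000 adult resident person-years for 2016-2020, using national adult counts by year, age and sex. Report it crude and standardized for age and sex to a named standard population.
- **Statistical analysis:** add exact 95% confidence intervals for both figures, binomial for the proportion of persons and Poisson for the crude rate, and a matching interval for the standardized rate.
- **Caveat:** state that cases are found only through insurance-fund codes, and that the death registry is consulted only for patients already included. The rate may therefore undercount relative to the cohort with 87% autopsies.

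The cost is one aggregate population table, some extra analysis and wording changes in three sections. No new patient data are needed.

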#### Database

The exact data that will be collected are shown in Annex 1.

All data will be entered in a Microsoft Excel database. The data will be pseudonymised - each patient will be assigned a unique study-ID. The key, to identify patients will be stored separately from the database on a secure server of Tartu University Hospital in a password protected file and can be accessed only by the principal investigator. Database will be stored separately from the key on a server of Tartu University Hospital in a password protected file and can be accessed by study investigators.

#### Statistical analysis

The study population will be described using common statistics (minimum, maximum, mean with standard deviation or median with interquartile range, standard error). The software package Statistica version 13.3 (TIBCO Software, California, USA) will be used for statistical calculations.

## **Ethical Considerations**

Our study is retrospective and descriptive, there is no intervention and researchers do not intercede.

### Data protection

In the study it is necessary to use personalized medical data, because queries from different registries are made using the personal identification code. The study aims cannot be fulfilled using anonymous data.

Data will be processed without the data subject's consent. Asking for informed consent is not possible as AMI has high mortality and most of these patients are not available for asking informed consent. Omitting these patients would seriously decrease the quality of the study.

Measures to safeguard the fundamental rights and the interests of the data subject:

- From Estonian Health Insurance Fund and Estonian Causes of Death Registry all data will be sent in encrypted form and will be decrypted by the principal investigator.
- Only pseudonymised data will be entered in the database. Each patient will be assigned a unique study-ID. The key, to identify patients will be stored separately from the database on a secure server of Tartu University Hospital in a password protected file and can be accessed only by the principal investigator. Database will be stored separately from the key on a server of Tartu University Hospital in a password protected file and can be accessed only by study investigators.
- Medical case files will not be sent via Internet or post. The principal investigator will go to the hospitals and enter the data to the database there.
- Only pseudonymized data will be used for data analysis and publication of results.
- The key to identify patients will be destroyed 3 years after the end of the study (31.12.2025)
- After the key is destroyed the database becomes anonymous. The anonymous database will be kept for 15 years.

Data controller: University of Tartu.

The collected data are going to be used only for publishing scientific articles about acute mesenteric ischemia. No information that allows identification of the study subjects will be published.

Data will not be used for financial purposes.

The Study has been approved by Research Ethics Committee of the University of Tartu (337/T-20). Approval of Estonian Committee of Bioethics and Human Research will be obtained.

### Data that will be collected

1. General
  - a. Gender (M/F)
  - b. Age (y)
  - c. Hospital
2. Health condition
  - a. Disability (no need of assistance/needs/No information(NI))
  - b. Consciousness (Adequate/Disturbed/No contact/NI)
  - c. Weight (kg/NI)
  - d. Height (cm/NI)
  - e. BMI (kg/m^2)
  - f. Smoking (yes/no/NI)
3. Diagnoses
  - a. Atrial Fibrillation (yes/no/NI)
  - b. Atherosclerosis (yes/no/NI)
  - c. Hypertonic disease (yes/no/NI)
  - d. Hypercholesterolemia (yes/no/NI)
  - e. Previous myocardial infarction (yes/no/NI)
  - f. Previous thromboembolic events (yes/no/NI)
  - g. Artificial heart valve (yes/no/NI)
4. Diagnoses II
  - a. Important main or accompanying pathology
5. Medications
  - a. Anticoagulant drugs (yes/no/NI)
  - b. Antiplatelet drugs (yes/no/NI)
  - c. Statins (yes/no/NI)
6. Emergency Department
  - a. Arrival to hospital (by self, ambulance)
  - b. Occurred during hospital treatment (then yes here, and previous is left empty)
  - c. Arrival to hospital since the beginning of symptoms (hours (h)/unclear)
  - d. Time from admission to hospital since CT-scan (h)
  - e. Time from beginning of symptoms to diagnosis (h)
  - f. Time from arrival to hospital since diagnosis (h)
7. Laboratory tests
  - a. Lactate (mmol/l/NI)
  - b. WBC (x 10E9/L/NI)
  - c. Creatinine (mcmol/l/NI)
  - d. eGFR (mL/min/1,73m^2/NI)
  - e. BE (mmol/l/NI)
  - f. ASAT (U/L/NI)
  - g. Amylase (U/L/NI)
  - h. D-dimers (mg/L/NI)
  - i. Troponin T (ng/L/NI)

8. Radiography
  - a. What was the first radiographic study (x-ray, US, CT/NI)
  - b. Was there a CT-scan made (yes/no)
  - c. Phase of enhancement in CT-scan (no contrast media, portal venous, arterial, delayed phase)
  - d. Radiologist diagnosed AMI (yes/no)
  - e. Time between CT-scan and the response by radiologist (min)
9. Type of AMI
  - a. Arterial embolism (a. mes. sup. – aortic ostium, until separation of a. colica media, peripheral)
  - b. arterial thrombosis (a. mes. sup. – aortic ostium, until separation of a. colica media, peripheral)
  - c. arterial non specified (a. mes. sup. – aortic ostium, until separation of a. colica media, peripheral)
  - d. Venous
  - e. NOMI
  - f. Other location (truncus coeliacus or a. mes. inf.)
  - g. Unclear
10. Treatment
  - a. Time from beginning of symptoms to treatment (h)
  - b. Time from diagnosis to treatment (h)
  - c. Surgical tactics (diagnostic laparoscopy, diagnostic laparotomy, therapeutic laparotomy, second-look tactics)
  - d. Vascular tactics (embolectomy, thrombectomy, endarterectomy, aortomesenteric shunt)
  - e. Gastrointestinal tactics (no need, resection with primary anastomosis, resection with stoma formation, resection without anastomosis and second look)
  - f. Intestinal resection (cm/NI)
  - g. Resection of colon (no need, right hemicolectomy, subtotal colectomy)
  - h. Endovascular treatment (aspiration of thrombus/embolism, ballondilatation, stent placement, thrombolysis, combined)
  - i. Conservative treatment
  - j. End-of-life care
11. Hospital treatment
  - a. Duration
  - b. End (discharged, death)
  - c. 30 day survival (alive/dead)
  - d. 90 day survival (alive/dead)
  - e. 180 day survival (alive/dead)
  - f. 360 day survival (alive/dead)

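### Annex 1 item 9 puts mechanism and vessel in one list, so an inferior mesenteric arterial occlusion cannot be recorded unambiguously by both

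*Combined protocol and SAP*

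**What the plan says.** The Background section divides AMI into arterial thrombosis, arterial embolism, venous thrombosis and non-occlusive ischemia (NOMI). All four are mechanisms, and vessel plays no part.

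In Study design and methods, under Study data, the occlusive case definition requires "thrombosis or embolism of the mesenteric arteries or thrombosis of the mesenteric veins". This is not limited to the superior mesenteric artery, and the NOMI criterion there names both the superior and the inferior mesenteric artery. The coeliac trunk is not named in either.

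Annex 1, item 9 has seven lettered options:

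- 9a is "Arterial embolism (a. mes. sup. – aortic ostium, until separation of a. colica media, peripheral".
- 9b and 9c repeat the same superior mesenteric sites for arterial thrombosis and for unspecified arterial disease.
- 9d is venous, 9e is NOMI and 9g is unclear.
- 9f is "Other location (truncus coeliacus or a. mes. inf", with no sub-option for mechanism.

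The secondary objective served by this item is "To describe the phenotype of AMI". The Statistical analysis section plans summary statistics only. It has no rule for counting 9f.

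**The concern.** Item 9 answers two questions in one list: what caused the ischemia, and which vessel was affected. For superior mesenteric disease both answers fit. For an arterial occlusion elsewhere they compete.

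What is at stake is the description of AMI by the protocol's own classification. The Sample size section justifies 500 patients partly by subgroups set out earlier in the text, and the only such listing is the mechanism split in the Background. The results are also meant to inform the design of a prospective study. If mechanism is missing for arterial cases outside the superior mesenteric artery, embolism and thrombosis are counted fully only for one vessel.

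**Working it through.** **Step 1: follow one eligible patient through the form.** Take an embolus in the inferior mesenteric artery that meets the clinical and CT or necrosis criteria.

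| Source | How the patient is classed |
|---|---|
| Background | Arterial embolism |
| Case definition | Eligible, as embolism of a mesenteric artery |
| 9a alone | Mechanism kept; no valid site |
| 9f alone | Site kept (shared with the coeliac trunk); mechanism lost |
| 9a and 9f together | Could equally be a superior mesenteric embolus plus disease in a second vessel |

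No row records both facts without ambiguity. The same holds for a thrombus, with 9b in place of 9a. Venous and NOMI cases are not caught, because 9d and 9e are their own options.

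**Step 2: can other fields restore the mechanism?** Items 10d and 10h (open vascular and endovascular procedures) give a hint, but only for patients who had such a procedure. In the national inpatient database cited in the Background, 3% had an attempted revascularization. Atrial fibrillation and atherosclerosis in item 3 are risk factors and do not establish the mechanism.

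**Step 3: bound the effect on a mechanism share.** The plan gives no figure to reproduce.

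Inputs:
- N = 500, from the Summary and the Sample size section.
- f, the fraction coded 9f only: not in the documents; assumed 1% to 10%.
- s, the true share of one mechanism: not in the documents; 40% is used for illustration.

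Formulas:
- 9f kept in the denominator: the recorded share lies between s − f (every 9f case has that mechanism) and s (none has). If the 9f cases have the same mix as the rest, it is s(1 − f).
- 9f left out of the denominator: the share lies between (s − f)/(1 − f) and s/(1 − f).
- Sampling error: 95% half-width = 1.96 × √(s(1 − s)/N).

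| f | Cases (500 × f) | Recorded share, 9f in denominator | Same mix | Recorded share, 9f excluded |
|---|---|---|---|---|
| 1% | 5 | 39.0% to 40.0% | 39.6% | 39.4% to 40.4% |
| 2% | 10 | 38.0% to 40.0% | 39.2% | 38.8% to 40.8% |
| 5% | 25 | 35.0% to 40.0% | 38.0% | 36.8% to 42.1% |
| 10% | 50 | 30.0% to 40.0% | 36.0% | 33.3% to 44.4% |

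Half-width at s = 40%: 1.96 × √(0.4 × 0.6/500) = 4.3 points. At s = 30% it is 4.0 points and at s = 20% it is 3.5 points. The worst-case understatement therefore exceeds sampling error only when f is above about 4%.

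**The case against.** The strongest reply is that the protocol never says item 9 is a single choice. In most of Annex 1 each letter is a separate field with its answers in brackets. Where one field excludes another the annex says so, as in 6b. Read that way, 9a and 9f can both be completed and the mechanism is kept. This stands as far as it goes: loss of mechanism is not certain. It does not cure the form, because the pair 9a plus 9f then has two meanings, and item 9 has no instruction to tell them apart.

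A reader might go further and infer that the phenotype shares will be wrong, and that treatment and survival by mechanism inherit the error. The documents do not support this. Phenotype is not defined, no mechanism shares or denominator are planned, and no analysis of treatment or outcome by mechanism is specified. A table that shows 9f as its own labelled row would be correct as labelled.

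It can also be said that the loss is recoverable, since the identification key is kept until 31.12.2025 and the charts can be read again. That is true until then. But the principal investigator enters data on site at each hospital, so a re-read means going back. After the key is destroyed the cases can no longer be traced, although the database is kept for 15 years.

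**Conclusion.** The point holds as a data-collection defect of limited size. As item 9 is written, arterial occlusion of the inferior mesenteric artery cannot be recorded unambiguously by both mechanism and site, so a split by the Background classification may understate embolism or thrombosis. With 9f kept in the denominator, the understatement of any one share is at most the fraction coded 9f. The range of 1 to 10 points rests entirely on an assumed 1% to 10%, and at 1% to 2% it lies within sampling error.

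The effect is confined to a secondary, descriptive objective. Case counting does not depend on item 9, so the primary incidence objective is untouched. Whether isolated coeliac cases are affected at all is open, because the case definition does not name that vessel.

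**What to change.** Replace item 9 with two fields.

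1. Mechanism, one value per patient: embolism, thrombosis, arterial non-specified, venous, NOMI, unclear.
2. Vessel or vessels involved, more than one allowed: superior mesenteric artery with its three existing segments, inferior mesenteric artery, coeliac trunk, mesenteric vein, none.

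Drop 9f as a type. State in the Statistical analysis section that mechanism shares come from the first field and location from the second. Reconcile the coeliac trunk in 9f with the occlusive case definition, so that it is clear whether isolated coeliac occlusion counts as a case.

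The same imaging, operation and autopsy reports supply both fields, so no new data source is needed. Before data entry the cost is close to nil. The documents do not say whether entry has begun. If it has, cases already coded 9f, alone or with another option, need a second look at the charts while the identification key still exists.
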